### **7. Ethics consideration:**

The present research will be conducted after the approval of the Research Ethics Committee (REC) of the faculty of Dentistry, Suez Canal University. Ethical considerations regarding patient well-being and confidentiality will be undertaken by the researcher and informed written consent will be signed by the patients before commencing the study explaining all clinical examinations, procedures, and follow-up. (Attached appendix I)

### **8. Time Plan**

**Starting** after approval of the ethical committee and faculty council.

**Ending** after 24 months.

Activity/Month	-	2	3	4	5	6	7	8	9	10	11	12	13	14	15	16	17	18	19	20	21	22	23	24
Patient selection																								
Material application																								
Statistics																								
Writing																								
Revision																								

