## II: Methods:

### II- 1 Study Setting:

A randomized controlled double-blinded clinical trial will be conducted where both patient and examiners will be blinded to the group assignment. Patients of age group 21–45 years (**Hirani et al, 2018**) will be selected where each patient should have two ocluso- mesial cavities. Patients will be recruited from the outpatient clinic of Conservative Dentistry department in the Faculty of Dentistry, Suez Canal University. During the initial examination, the purpose and the method of the research will be explained to the patients and a written informed consent will be assigned by each individual.

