#### **II-6- Evaluation of the wear resistance:**

A digital impression will be taken immediately after restoration (T0) using an intraoral scanner (Helios 600 intraoral scanner, Eighteeth, Changzhou, China). To ensure optimal performance and accuracy, the scanner underwent regular calibration before scanning each patient, following the manufacturer's recommendations. During the scanning procedure, the device will be positioned at a 90° angle for the occlusal surface and at 45° angles for both buccal and lingual surfaces. Later on, each restoration will be examined at standardized follow-up periods (Table 2 and 3); six months (T1), twelve months (T2), eighteen months (T3) and twenty-four months (T4). The 3D impressions will be analyzed using a software (Geomagic software, 3D Systems Inc., USA) program and the impressions of each two consultative visits will be superimposed to determine the wear volume loss (mm^3). (Bronkhorst et al, 2022)

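### The 24-month project end in the Time Plan leaves no room for a wear scan due 24 months after restoration, or for analysing it

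*Protocol*

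**What the plan says.** Section 8 (Time Plan) gives the start as "after approval of the ethical committee and faculty council" and, on the next line, the end as "after 24 months". The chart below has a month axis that stops at 24. Its rows include "Patient selection" and "Material application", followed by statistics, writing and revision.

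The wear follow-up runs on a different clock. Section II-6 sets its origin at restoration: "A digital impression will be taken immediately after restoration (T0"). Later scans follow at 6, 12, 18 and 24 months (T1 to T4). The Abstract and Table 2 give the same schedule. Section II-6 obtains wear volume by superimposing scans from pairs of visits. Section 3 asks for the comparison at two years.

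Three statements bear on the time before any tooth is restored:

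- Section 7: "The present research will be conducted after the approval of the Research Ethics Committee (REC").
- Section 7: "informed written consent will be signed by the patients before commencing the study".
- Section II-1: "Patients will be recruited from the outpatient clinic of Conservative Dentistry department".

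**The concern.** The project length and the last follow-up interval are both 24 months, but they start at different points. The project starts after approval. Each patient's wear follow-up starts when that patient's teeth are restored, which comes after approval, recruitment, consent and treatment. The two can end together only if every restoration is placed at project start, and even then nothing is left for analysis.

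T4 is the visit that answers the two-year question in Section 3. If Section 8 were taken at its word, the project would close before T4 for any patient restored after the start date. The more likely outcome is an overrun, because Section 8 is a timetable and not a stopping rule. Even so, the stated end should not be open to being read as the date on which wear follow-up or analysis closes.

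**Working it through.** **Inputs**

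- Project start: after approval (Section 8). Call this month 0.
- Stated project end: month 24 (Section 8).
- T0: immediately after restoration (Section II-6).
- T4: 24 months after restoration (Section II-6, Abstract, Table 2).
- t: months from project start to restoration, t ≥ 0. The text gives no figure for t, so it is varied below.
- a: months needed after T4 for superimposition and the final wear analysis, a ≥ 0. Also not given.

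**Formulas**

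- Calendar month of T4 = t + 24.
- Overrun of T4 past the stated end = (t + 24) − 24 = t.
- Time left for final analysis inside the plan = 24 − (t + 24) = −t.
- Project length needed = t + 24 + a, with t taken at the last restoration.

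**Can the stated 24 months be reproduced?** Setting t + 24 + a = 24 gives t + a = 0, so t = 0 and a = 0. The stated length fits only if every patient is restored at project start and the final analysis takes no time. Sections 7 and II-1 rule out t = 0 in practice, since patients must be recruited from the clinic and give consent first. The T4 wear value cannot exist before the T4 scan, so a = 0 is not realistic either.

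**Assumed lags**

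| t (months, assumed) | T4 at month | T4 past stated end by | Time left for final analysis |
|---|---|---|---|
| 0 | 24 | 0 | 0 |
| 1 | 25 | 1 | −1 |
| 3 | 27 | 3 | −3 |
| 6 | 30 | 6 | −6 |

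**Illustration from the chart ticks.** The chart is damaged in the text available (rows of 19 or 13 boxes under 24 columns), so the conclusion does not use it. If the ticks are right, placement runs over months 2 to 7. With month k covering elapsed time k − 1 to k, t lies between 1 and 7. T4 then falls between 1 + 24 = 25 and 7 + 24 = 31 months, an overrun of 1 to 7 months before any analysis time. At month 24, the earliest restorations would have 24 − 1 = 23 months of follow-up. The latest would have 24 − 7 = 17 months, short even of T3 at 18.

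**The other reading.** Suppose the 24 months mean follow-up per patient. They then agree with T4. But Section 8 would state no project end, and its 24-month axis would still have to hold selection, placement, 24 months of follow-up and the final analysis. That needs t + 24 + a, which exceeds 24 for any t + a above 0.

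**The case against.** The strongest reply is that the conflict depends on one reading of a very short line. Section 8 does not say 24 months from approval, or total duration. The figure equals the T4 interval and the two-year horizon of Section 3, so it may simply restate the follow-up length. Consent before the study commences would also fit a clock that starts after enrolment. The chart shows no row for follow-up visits, so it may be only a coarse activity plan. Finally, nothing in Section 8 truncates T4 or changes the planned comparison. T4 is stated consistently wherever the visits are defined, and no bias or loss of power follows from the timetable alone.

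Part of this stands. The follow-up reading is possible and would remove the conflict between visits. The tick-based figures should carry no weight, and the text shows only that any positive lag overruns, not by how much. The practical consequence is an overrun rather than a demonstrated loss of data.

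The rest does not remove the point. Section 8 pairs a start after approval with an end, over an axis that includes selection and placement, so project time is the likelier meaning. Nothing in the Protocol adds time beyond month 24 or says that the 24 months run from the last restoration. On either reading Section 8 needs correcting.

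**Conclusion.** The concern holds. Read as project time, the stated end is inconsistent with the Protocol's own visit schedule. T4 falls t months late for a patient restored t months after the start, and the time left for the final wear analysis is 0 months at best and negative otherwise. For assumed lags of 1 to 6 months, T4 falls at months 25 to 30, with analysis and writing still to come.

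The conclusion rests on the stated start, the stated end and the definition of T4, and on reading the 24 months as total duration; confidence is medium because of that last step. The error should be corrected because it affects the visit that answers the main wear question. It does not by itself show that T4 data will be lost.

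**What to change.** Reconcile Section 8 with Section II-6:

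- State what the time plan counts from.
- State that the study ends when the last restored patient has completed T4, 24 months after restoration.
- Extend the chart to that date, and place the final wear analysis and writing after it.
- If the 24 months were meant as follow-up length, say so and give the project end separately; the same end definition then applies.

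Leave the two-year question in Section 3 and the visit schedule as they are.

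The cost is a later stated end date, by the lag to the last restoration plus the time for analysis and writing (t + a in the notation above). No visits or procedures are added, because T4 is already planned for every patient.

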### **9. Research Estimated Budget in Egyptian Pound**

Supplementary						Publications	Total
Material	Scanning	Softwares	Tests	Statistics	Others (Designing)	International publication	
15,000	5000	53000	12000	5000	-	10,000	100000

#### **5- Grade of protocol:**

\*M.D.Sc. ( ) \*Ph.D. ( ) \*Doctorate degree (D.D.Sc.) (✓) \*Other ( )

\*Domestic (✓) \*Multi-Centre within Egypt ( )

\*International ( )

**6- Title of the research: Clinical Evaluation of Wear  
Resistance and Bioactivity of Self cured Bioactive Resin  
Composite.**

#### **7-Type of the research:**

\*Drug trial ( ) \*Surgical technique ( ) \*Investigative technique (✓)

\*Devise study ( ) \*Survey study ( ) \*Blood sampling ( )

\*Review of old records ( )

**8-Subjects of research:**

\*Children (< 18 years): (  ) \*Adults (>18 years) (  )

\* Vulnerable groups (yes) or (no)

**9-Request is being made to waive (give-up) informed consent:**

Yes: (  ) No: (  )

**10- The research is for the good of society:**

Yes: (  ) No: (  )

**11-Study design:**

a-Phase type

I: (  ) II: (  ) III: (  )

b-Randomization:

Yes: (  ) No: (  )

c-Placebo:

Yes: (  ) No: (  )

d-Genetic sampling:

Yes: (  ) No: (  )

e-Other: Yes: (  ) No: (  )

**12-Facilities for the research are available:**

Yes: (  ) No: (  )

**13- List the risks of the study:**

No risks have been reported.

**14- List the potential benefits, if any, to the subjects:**

The patient will receive the treatment with no fees.

**15-Are the risks reasonable to the potential benefits to the subjects, if any, or to the knowledge to be gained?**

Yes: (✓)      No: ( )

**16-Privacy and confidentiality of subjects are assured**

Yes: (✓)      No: ( )

**17-The subject of the research could quit at any time without penalty or loss of any benefits to which they would otherwise be entitled**

Yes: (✓)      No: ( )

---

---

